Study Procedures	
After providing informed consent, patients will undergo screening for eligibility to participate in the study. Screening will start within 21 days prior to dosing with the exception of tumor burden assessment (e.g., CT scan) which may have been performed within 28 days.
 
A cycle of dosing is defined as 28 days. In each dose escalation cohort, patients will receive their assigned dose of pexidartinib on the morning of Cycle 1 Day 1 (C1D1) and will remain in the outpatient clinic for 8 hours for observation and pharmacokinetic (PK) sampling. For QD dosing, PK samples will be collected prior to dosing and 0.5, 1, 2, 4, and 8 hours following dosing. The initial dosing regimen of pexidartinib will be once daily by oral administration. A twice daily dosing regimen may be used in subsequent cohorts, depending on the PK data obtained from once-daily dosing in the first cohort. For BID dosing, PK samples will be obtained predose (AM) and 1, 2, 4, 7 hours postdose on C1D1. The second dose will then be administered, and a 1 hr post dose sample will be obtained (8 hours after the first dose). Patients will return to the clinic on the morning of C1D2 and C1D8 prior to dosing on that day for evaluation and blood draw to obtain the predose PK time-point (approximately 12 hours after the previous evening dose for a BID dosing regimen). Patients will continue to dose pexidartinib once or twice daily and return to the clinic for evaluation on C1D8. On C1D15 and C1D16 (± 2 days), blood samples will be obtained once again for measurement of pexidartinib PK, using the same sampling times as on C1D1 and C1D2. Patients will return to the clinic on C2D1 for evaluation. If pexidartinib has been well tolerated and there has been no clinical evidence of disease progression, continued dosing will be permitted. Patients with solid tumors will be monitored for response and disease progression with tumor burden assessments every two months.
 
In selected cohorts, 3–6 patients will be treated with a pexidartinib dose of 100 mg QD during a one-week run-in period before increasing to the full dose for that cohort, in order to profile the pharmacodynamic (PD) dose response activity of pexidartinib at doses below 300 mg QD. Similarly, 3–6 patients will be treated with a pexidartinib dose of 200 mg QD during a one-week run-in period. After baseline predose blood is obtained on C1D(-7), the first dose of 100 mg or 200 mg will be administered, and PK samples will be obtained. Patients will return to the clinic the following AM (C1D(-6)) and 2 days later (C1D(-4)) for blood draws for PK and the PD biomarkers. They will then return for C1D1 for initiation of dosing at the full dose for that cohort.

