
	
At the recommended Phase 2 dose (RP2D), a total of six Extension cohorts of approximately 10 patients each (except for the miscellaneous cohort, which will include up to approximately 20 patients) will be enrolled and followed for safety and tumor response as assessed by radiographic imaging. These six cohorts consist of 1) mucoepidermal carcinoma (MEC) of the salivary gland, 2) pigmented villo-nodular synovitis (PVNS), 3) GIST, 4) anaplastic thyroid carcinoma (ATC), 5) solid tumors with documented malignant pleural or peritoneal effusions, and 6) miscellaneous tumor types for which a scientific rationale exists for treatment with pexidartinib. For PVNS patients, imaging will also be performed approximately 30 days and 12 weeks after last study drug.
 
Patients will be monitored throughout the study for adverse reactions to the drug formulation and/or study procedures.
 
For the dose escalation cohorts, clinical laboratory assessments (hematology, chemistry, and urinalysis) will be performed at screening, C1D8, C1D15, and at the beginning of each subsequent 28 day cycle for those patients who continue on therapy, and at study completion or upon early withdrawal. Urinary, blood and serum biomarkers of response will be evaluated on C1D1, C1D8, and C2D1.
 
Blood pressure, respiratory rate, pulse, and temperature will be measured at screening and predose at each study visit except for C1D2 and C1D16. Blood pressure and pulse will also be monitored at 1 and 4 hours postdose on C1D1.
 
Triplicate ECGs (within 2 minutes apart) will be obtained at screening, prior to dosing on C1D1, and at 2, 4, and 6 hours postdose on C1D1 and C1D15.
 
A physical examination will be performed for each patient at screening, C1D8, C1D15, C2D1, and then monthly while continuing study drug administration, and at study completion or upon early withdrawal.
 
For the Extension cohorts, a simplified study plan will be used, as detailed in the study flow chart. Patients enrolled after the implementation of Amendment 8 will complete two patient reported outcome (PRO) instruments: the Western Ontario and McMaster Universities Osteoarthritis Index (WOMAC[®]) and the Numeric Rating Scale (NRS) for PVNS Symptoms questionnaire. These will be completed predose at the clinic on C1D1, C1D15, C2D1, and monthly thereafter while continuing study drug administration, and at the End of Study visit. In addition, these patients will complete the NRS for PVNS Symptoms questionnaire on an outpatient basis for 6 consecutive days (Day -6 to Day -1) prior to each monthly clinic visit on C1D1, C2D1, C3D1, etc. while continuing study drug administration.
 
The visit schedule for extension patients will be changed to every 12 weeks/3 cycles (with an option to complete on-site visits every 24 weeks/6 cycles if local safety laboratory testing and telephone check-ins are completed 12 weeks after each on-site visit) after a subject has completed at least C40 and if there are no ongoing safety or treatment issues. Imaging will be performed every 24 weeks/6 cycles, and PK, Urinalysis, and ECOG will be discontinued.

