Dosage and Regimen	
The proposed starting dose is 200 mg QD. A BID dosing regimen may be used in subsequent cohorts, pending review of the PK from the initial cohort.
 
Cohorts of patients with solid tumors will be enrolled using 100% dose increments in the absence of drug-attributable Grade 2 toxicity. In each cohort (and following the one-week run-in period for applicable patients), the first patient will be observed for at least one week before additional patients in that cohort are treated with pexidartinib. Following the one-week run-in period for applicable patients, upon the occurrence of Grade 2 or greater drug-attributable toxicity, in the absence of dose limiting toxicity (DLT), dose escalation will proceed sequentially by 50% increments. From that point forward, the standard "3+3" design will be used. Following the one-week run-in period for applicable patients, if DLT is observed in one patient at a given cohort, at least 6 patients will be treated at that dose. Following the one-week run-in period for applicable patients, if DLT is observed in 2 or more of 6 patients at a dose level, then the next lower dose level will be expanded or an intermediate dose level will be introduced. The MTD is defined as the dose at which ≤ 1 of 6 patients experience a DLT during Cycle 1, with the next higher dose having at least 2 of the up to 6 patients experiencing a DLT during Cycle 1. If no DLT is observed, the recommended dose for further evaluation will be established based on toxicity, PK, and convenience of dosing in approximately 3–6 patients treated at that dose. Dose escalation will only be permitted if adequate safety and tolerability have been demonstrated at the previous lower dose for 28 days.
 
The dosage for the Extension cohorts will be the RP2D level of 1000 mg/day, using a BID regimen.

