PD Parameters	
 • Morning urine: N-Telopeptide of Type I Collagen (NTX) and C-Telopeptide of Type II Collagen (CTX-II) • Serum markers: Serum C-Telopeptide of Type I Collagen (CTX), Procollagen Type I Intact N-Terminal Propeptide (PINP), Bone-specific Alkaline Phosphatase (BAP), Tartrate-Resistant Acid Phosphatase (TRAP 5b), Interleukin-6 (IL-6), Interleukin-1β (IL-1β), Matrix Metalloproteinase 3 (MMP-3), Erythrocyte Sedimentation Rate (ESR), C-Reactive Protein (CRP), Colony-Stimulating Factor-1 (CSF-1) • Blood markers: Circulating Tumor Cells (CTC), CD14+/CD16+ monocytes

TRIAL FLOW CHART (no Run-in Period)

EVENT ▼	STUDY DAY ► Day -21 to -1	C1 D1 ¹	C1 D2	C1 D8	C1 D15	C1 D16	C2 D1	D1 of C3+ ²	End of Rx ³
Informed Consent	X								
Medical History	X								
Height/Weight	X								
Physical Exam	X			X	X		X	X	X
Chem, Hem, Coag, UA	X			X	X		X ¹³	X ¹³	X
TSH	X						X	X	X
ECG ⁴	X	X			X				
Vital Signs ⁵	X	X		X	X		X	X	X
Plasma for PK ⁶		X	X	X	X	X	X	X	
Pregnancy Test ⁷	X								
ECOG Performance Status Assessment	X						X	X	X
Serum and Urine for Biomarker Assessment ⁸		X		X			X		
Circulating Tumor Cell (CTC) Assessment ⁹		X					X		
CD14+/CD16+ monocyte Assessment ¹⁰		X		X					X
Radiographic Assessment of Tumor Burden ¹¹	X							X	
Test article compliance		X	X	X	X	X	X	X	X
Concomitant Medications	X	X	X	X	X	X	X	X	X
Adverse Events ¹²		X	X	X	X	X	X	X	X

C = cycle; D = day; CxDx = Cycle x, Day x; UA = urinalysis

For footnotes, see [Explanation of Subscripts](#) below.

TRIAL FLOW CHART (with one-week Run-in Period)

STUDY DAY▶ EVENT▼	Day -28 to -7	C1 D -7	C1 D -6	C1 D -4	C1 D1¹	C1 D2	C1 D8	C1 D15	C1 D16	C2 D1	D1 of C3+²	End of Tx³
Informed Consent	X											
Medical History	X											
Height/Weight	X											
Physical Exam	X						X	X		X	X	X
Chem, Hem, Coag, UA	X						X	X		X ¹³	X ¹³	X
TSH	X									X	X	X
ECG ⁴	X				X			X				
Vital Signs ⁵	X	X			X		X	X		X	X	X
Plasma for PK ⁶		X	X	X	X	X	X	X	X	X	X	
Pregnancy Test ⁷	X											
ECOG Performance Status Assessment	X									X	X	X
Serum and Urine for Biomarker Assessment ⁸					X		X			X		
Circulating Tumor Cell (CTC) Assessment ⁹		X								X		
CD14+/CD16+ monocyte Assessment ¹⁰		X	X	X	X		X					X
Radiographic Assessment of Tumor Burden ¹¹	X										X	
Test article compliance		X	X	X	X	X	X	X	X	X	X	X
Concomitant Medications	X	X	X	X	X	X	X	X	X	X	X	X
Adverse Events ¹²		X	X	X	X	X	X	X	X	X	X	X

C = cycle; D = day; CxDx = Cycle x, Day x; Tx = treatment; UA = urinalysis

Explanation of Superscripts:

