13.2 Run-In Period (Selected Cohorts) – Cycle 1 Day(-7), Day(-6), and Day(-4)

1. All 3 days: Recording of concomitant medications and adverse events.

2. All 3 days: Vital signs (sitting blood pressure, pulse rate, and respiratory rate and oral temperature [°F]).
3. All 3 days: Pre-dose blood sample collection for PK analysis and response biomarkers.
4. C1D(-7): Post-dosing blood collection for PK analysis.

13.3 Pre-Treatment (Baseline): Cycle 1 Day 1

Patients will return to the clinic on C1D1 and will undergo the following procedures:

1. Recording of concomitant medications.
2. Vital signs (sitting blood pressure, pulse rate, and respiratory rate and oral temperature [°F]).
3. Standard 12-lead ECG in triplicate 2 minutes apart.
4. Pre-dose blood sample collection for PK analysis and response biomarkers.
5. Pre-dose morning urine collection for response biomarkers.

13.4 Post-Treatment: Cycle 1 Day 1 and Cycle 1 and Day 2

On C1D1, each patient will receive the assigned dose of test article. AE monitoring will be continuous. Vital signs, ECGs, laboratory evaluations, and PK sample collections will be completed at designated times during the study (see [Trial Flow Charts](#)). The blood sample for PK analysis should be collected at the scheduled time, within the windows noted in the PK section. ECG in triplicate will be repeated at 2, 4, and 6 hours after administration of study drug. Pulse and blood pressure will be repeated at 1 and 4 hours post administration of study drug on C1D1. Patients will return to the clinic on the morning of C1D2 prior to dosing on that day for evaluation and blood draw to obtain the predose PK time-point (approximately 12 hours after the previous evening dose for a BID dosing regimen).

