13.5 Cycle 1 Day 8 ± 1 Day

Patients will return for evaluation of AEs, concomitant meds, vital signs, physical exam, clinical laboratory values, and collection of serum and morning urine for biomarker assessments. A predose blood sample for PK and as well as predose blood samples for response biomarkers will be obtained, as well as a predose morning urine for response biomarkers (see [Trial Flow Charts](#), pp. 16–20).

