16.4 Dose Escalation

At least three and up to six patients will be enrolled in each dose level using 100% dose increments for each level in the absence of Grade 2 or greater drug-attributable toxicity. In each cohort (and following the one-week run-in period for applicable patients), the first patient will be observed for at least one week before additional patients in that cohort are treated with pexidartinib. Following the one-week run-in period for applicable patients, upon the occurrence of Grade 2 or greater toxicity, in the absence of DLT, dose escalation will proceed sequentially by up to 50% increments. Following the one-week run-in period for applicable patients, if one DLT is observed in one of the first 3 patients during the first cycle in a given cohort, at least 6 patients will be treated at that dose. Following the one-week run-in period for applicable patients, if DLT is observed in 2 or more of 6 patients at a dose level, then the next lower dose level will be expanded or an intermediate dose level will be introduced. Dose escalation will only be permitted if adequate safety and tolerability have been demonstrated at the previous lower dose for 28 days for the first 3 patients. The DLTs observed in all patients in the first cycle will be taken into account when evaluating the safety of a given dose level to support dose escalation or selection of a recommended Phase 2 dose. Dose escalation decisions will be made during teleconferences attended by the medical monitor and appropriate personnel from all participating sites.

Dose Limiting Toxicities during the first 28 days of treatment are defined as follows:

- Any CTCAE (version 4) Grade 4 toxicity (Grade 4 neutropenia for ≥ 3 days)
- Any CTCAE Grade 3 toxicity other than Grade 3 lymphopenia
- CTCAE Grade 2 vomiting within 2 hours of study drug administration on 3 consecutive days despite optimal anti-emetic therapy
- If, for any reason, either the Principal Investigator or Sponsor deems further dose escalation inappropriate

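### Run-in patients go to full dose with no on-drug safety panel, the DLT period has two possible starts for them, and no laboratory result is required before a cohort's second patient is dosed

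*Combined protocol and SAP*

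**What the plan says.** **Laboratory schedule.** For the escalation cohorts the synopsis (Study Procedures) states that "clinical laboratory assessments (hematology, chemistry, and urinalysis) will be performed at screening, C1D8, C1D15, and at the beginning of each subsequent 28 day cycle". Both escalation flow charts agree: the row "Chem, Hem, Coag, UA" is marked at screening and next at C1D8. In the run-in chart it is blank at C1D(-7), C1D(-6), C1D(-4), C1D1 and C1D2. Section 13.5 gives the window, "Cycle 1 Day 8 ± 1 Day". Section 13.4 mentions laboratory evaluations on C1D1 and C1D2 but refers to the flow charts for their timing, so it adds no panel.

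**Run-in.** Selected patients take 100 or 200 mg QD for one week. Section 13.2 lists their blood sampling: "All 3 days: Pre-dose blood sample collection for PK analysis and response biomarkers". The synopsis continues: "They will then return for C1D1 for initiation of dosing at the full dose for that cohort". Section 13.3 lists predose blood on C1D1, also for PK and response biomarkers only.

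**First patient in a cohort.** The synopsis (Dosage and Regimen) states that "the first patient will be observed for at least one week before additional patients in that cohort are treated with pexidartinib". Section 16.4 repeats the rule: "In each cohort (and following the one-week run-in period for applicable patients), the first patient will be observed for at least one week". Neither place makes a laboratory result part of that observation.

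**DLT period.** Dosage and Regimen in the synopsis, and Section 16.4, apply the Grade 2 and DLT rules once the run-in week is over. Duration of Study limits MTD determination to 28 days counted from drug administration, and Stopping Rules counts DLTs over 28 days of pexidartinib. Neither of these two excepts the run-in.

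**Baseline.** Section 24.1 takes the last value on or before the first pexidartinib dose.

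**The concern.** Escalation depends on small counts. One DLT in three patients leads to expansion, two in six end escalation at that level, and a single drug-attributable Grade 2 toxicity changes the dose increments from 100% to 50%. The DLT list covers Grade 3 and 4 toxicities with specific rules for neutropenia and lymphopenia, so some of these events will be seen only in a laboratory panel.

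For run-in patients, the only laboratory value before C1D8 is from screening, before any drug. If C1D8 shows an abnormality, nothing in the data shows whether it arose on the run-in dose or on the full dose. Whether it should count against the full dose is also unclear, because the plan gives two starts for the DLT period.

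For the first patient of a cohort, the observation week protects the later patients against laboratory toxicity only if a result is in hand when it ends. One week is a relevant interval. In the 7-day rat study (Section 6.4.1) blood counts fell and liver tests rose, and Section 7.1 bases escalation planning on marrow effects and the resulting fall in white cell counts.

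**Working it through.** The plan states no figure to reproduce here. The check counts elapsed days on the flow charts, which have no Day 0.

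**1. First on-drug panel against the observation week.** Seven full days after C1D1 end on C1D8.

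| Panel drawn | Days since C1D1 | Position | Days since C1D(-7), run-in patients |
|---|---|---|---|
| Day 7 | 6 | inside the week | 7 + 6 = 13 |
| Day 8 | 7 | the day the minimum week ends | 7 + 7 = 14 |
| Day 9 | 8 | after the minimum week | 7 + 8 = 15 |

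One of the three permitted days falls inside the minimum week, one on its last day and one after it. A result before the second patient is dosed is therefore possible, but neither assured nor required.

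**2. Run-in.** C1D(-7) to C1D1 is 7 days on drug with no safety panel. The first on-drug panel comes 13 to 15 days after first drug and 6 to 8 days after the increase.

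**3. Longest interval from the screening panel to the first on-drug panel.**
- Without run-in (Day -21 to Day 9): 21 + 8 = 29 days.
- With run-in (Day -28 to Day 9): 28 + 8 = 36 days, of which 21 precede any drug and 15 are on drug.

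**4. The two DLT periods for a run-in patient.**
- Counted after the run-in: 28 days from C1D1, all at full dose.
- Counted from first drug, read literally: 28 days from C1D(-7), that is 7 run-in days and 28 − 7 = 21 days at full dose.

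The readings differ by 7 days at each end. An event in the run-in week counts under the second reading only. An event in the fourth week at full dose counts under the first only. The visit labels do not settle it, because the run-in visits are themselves numbered within Cycle 1 and Section 16.4 ties the MTD to DLTs in Cycle 1.

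**5. Laboratory reference.** Under Section 24.1 a run-in patient's baseline is the last value before C1D(-7), in practice the screening panel. No scheduled value marks the start of full dosing.

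**The case against.** The strongest objection is that the exposure is limited and supervised. Run-in doses do not exceed the 200 mg QD starting dose. Adverse events are recorded at all three run-in visits. Patients without a run-in start the same full dose directly, and both groups have their first panel 6 to 8 days after it. Escalation to the next level waits 28 days and so includes the C1D8 and C1D15 panels. The CRO and sponsor coordinate patient numbers and dose verification, a weekly or as-needed teleconference reviews cumulative safety data (Section 9.1), and extra tests are allowed (Section 18.0).

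This stands as a limit on the risk, but it does not close the gap. Extra testing is discretionary. The teleconference confirms expansion and escalation, with no stated laboratory condition on the second patient. The 28-day wait protects the next dose level, not the rest of the same cohort. None of it supplies a value at the run-in to full-dose transition.

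Three stronger readings are tempting and should not be drawn:
- A reader might infer that the observation week necessarily passes without a laboratory result. It need not: a Day 7 draw is allowed, and the week is a minimum.
- A reader might infer that DLTs count only after the run-in. Duration of Study and Stopping Rules, read literally, say otherwise.
- A reader might infer that most expected toxicity is laboratory-detected. The documents give no share. Vomiting is a named DLT, and the dog doses were cut after the first week for clinical signs (Section 6.4.2).

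It is also fair that this version already fixes an RP2D of 1000 mg/day and refers to responses seen in escalation. The added panel helps only run-in patients still to be enrolled; the DLT-period question also affects how existing run-in data are reported.

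**Conclusion.** The point holds for the run-in. Full dosing begins with no scheduled on-drug panel, the first such panel comes 13 to 15 days after first drug, and the two statements of the DLT period differ by 7 days at each end. For the first patient of a cohort, the supportable conclusion is only that no laboratory result is required before the second patient is dosed, and that some permitted draw days would leave none available at the end of the minimum week.

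The day counts rest on the flow charts and the Section 13.5 window, with discretionary tests set aside. A reader might want the probability that a run-in event is wrongly counted as a full-dose DLT. The documents give no rate for laboratory events beginning at the run-in doses. Such an event would also have to meet a DLT criterion and still be present at C1D8, so no probability is offered. The change is a cheap improvement in attribution and monitoring; nothing here shows that a dose decision was wrong.

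**What to change.** 1. In the run-in flow chart and Section 13.3, add the routine chemistry and hematology panel to the C1D1 predose blood draw that already takes place. Report it beside the Section 24.1 baseline, without replacing that baseline, so that the onset of Cycle 1 laboratory events can be read. Cost: one routine panel per run-in patient, with no extra visit.
2. Reconcile Duration of Study and Stopping Rules in the synopsis with Dosage and Regimen and Section 16.4 on when the DLT period starts for run-in patients. Cost: a text change. If escalation is complete, state in the report which period was used.
3. Reconcile the one-week observation in the synopsis and Section 16.4 with the C1D8 ± 1 day window in Section 13.5, stating whether that panel is part of the observation. The sponsor and investigators decide the rule. Cost: a text change, plus any wait for a result that the chosen rule entails.

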Stopping Rules	
For the dose escalation cohorts, two patients in any cohort of 6 patients with any of the following Dose Limiting Toxicities during the first 28 days of pexidartinib administration:
 
 • Any CTCAE (version 4) Grade 4 toxicity (Grade 4 neutropenia for ≥ 3 days) • Any CTCAE Grade 3 toxicity other than Grade 3 lymphopenia • CTCAE Grade 2 vomiting within two hours of drug administration on 3 consecutive days despite optimal anti-emetic therapy • If, for any reason, either the Principal Investigator or Sponsor deems further dose escalation inappropriate 
For the Extension cohorts, detailed guidance is provided in the protocol body for dose reduction criteria and discontinuation of therapy due to safety concerns.

Safety and Tolerability Assessments	
Physical examinations, vital signs, 12-lead electrocardiograms, adverse events, hematology, serum chemistry, and urinalysis will be used to assess safety and tolerability.

PK Parameters	
The PK profile of plasma pexidartinib will be analyzed by measurement of area under the plasma concentration-time curve [AUC_{0-t}, $AUC_{0-\infty}$], peak concentration (C_{max}), time to peak concentration (T_{max}), half-life ($T_{1/2}$), and terminal elimination rate constant (K_{el}).
 
Dose proportionality following study medication will be explored by analyzing natural log-transformed pharmacokinetic variables, AUC_{0-t}, $AUC_{0-\infty}$, and C_{max}, with a linear model including the natural log-transformed dose as a covariate. Dose linearity for AUC_{0-t}, $AUC_{0-\infty}$, and C_{max} will also be explored by a linear model.
 
PK assessments will be measured for each dose cohort of patients with correlations of C_{max} and AUC to any SAEs. Dose-response trends in C_{max} and AUC will be analyzed within each patient group for any suggestion of drug accumulation or alterations in PK based on concomitant medications.

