
- Day 1–16 apply to first cycle only.
- If well tolerated and no tumor progression; clinic visits, laboratories at one month intervals with radiographic assessment performed every two months.
- End of treatment or early withdrawal procedures should be completed within 30 days of the last dose of study drug and prior to initiation of any new therapy.
- Triplicate ECG's (within 2 minutes apart) at screening and prior to dosing on C1D1, and at 2, 4, and 6 hours postdose on C1D1 and C1D15.
- Blood pressure, respiratory rate, pulse, and oral temperature will be recorded predose and at each clinic visit noted; blood pressure and pulse will also be recorded 1 and 4 hours postdose on C1D1.
- For QD dosing, obtained predose (AM) and 0.5, 1, 2, 4, and 8 hours postdose on C1D(-7), C1D1 and C1D15, and predose on C1D(-6), C1D(-4), C1D2, C1D8, and C1D16. For BID dosing on C1D1 and C1D15, obtained predose (AM) and 1, 2, 4, and 7 hours postdose. The second dose will then be administered, and PK obtained 1 hour post the second dose (8 hours post the first dose). For BID dosing, no run-in is planned, with predose samples obtained on C1D2, C1D8, and C1D16. During continued dosing, obtained once every 4 weeks (predose). In the event of a DLT or SAE, a single blood sample should also be obtained within 48 hours.
- For women of child-bearing potential; at screening should be within 7 days of first dose of study drug.

- ⁸ Morning urine NTX and CTX-II and the following serum markers: CTX, P1NP, BAP, TRAP 5b, IL-6, IL-1 β , MMP-3, ESR, CRP, CSF-1.
- ⁹ Obtain blood sample for circulating tumor cells (CTC) predose (AM) on C1D1 and C2D1.
- ¹⁰ Obtain blood sample for CD14+/CD16+ monocytes predose (AM) on C1D1 and C1D8; if feasible, also obtain a sample 1 week after discontinuing study drug.
- ¹¹ Screening window for radiographic assessment of tumor burden is 28 days.
- ¹² Monitored throughout the study via safety assessments, observation, and participant reporting.
- ¹³ For all cycles after Cycle 1, a CBC with differential is required every 2 weeks (i.e., mid-cycle in addition to end of cycle).

TRIAL FLOW CHART – Extension Cohorts

EVENT ▼	STUDY DAY ►	Day -21 to -1¹	C1 D1	C1 D15 (±2 d)	C2 D1 (±7 d)	D1 of C3 to C40² (±7 d)	D1 of C40, C43, C46, etc.+² (±7 d)	End-of-Study/ Early Withdrawal³	12-Week Follow-up (LD + 12 wk +4 wk)⁴
Informed Consent		X							
Medical History		X							
Height		X							
Weight		X			X	X	X (unless remote)	X	
Physical Exam		X		X	X	X	X (unless remote)	X	

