24.3 Pharmacokinetic Analysis

A noncompartmental method of analysis will be used to analyze the plasma concentrations of pexidartinib. C_{\max} and the time to attain the C_{\max} (t_{\max}) will be determined directly from the observed data. The following PK parameters will be estimated, based on available data:

- Clearance
- Volume of distribution
- Area under the plasma/serum concentration-time curve (AUC)
- Elimination half-life

Pharmacokinetic assessments will be measured for each dose cohort of patients with correlations of C_{\max} and AUC to any SAEs. Dose-response trends in C_{\max} and AUC will be analyzed within each patient group for any suggestion of drug accumulation or alterations in PK based on concomitant medications.

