24.5 Statistical Analyses

Statistical analyses will be descriptive in general. Limited statistical comparisons for a dose effect may be made using analysis of variance. The dependent variables for assessing dose proportionality will be estimates of selected PK parameters.

No formal statistical analysis of data from the PRO instruments will be performed. Results for each instrument will be listed by dose. Change from baseline may be calculated, as appropriate. WOMAC data from patients with only upper extremity disease (e.g., PVNS of the elbow) may be excluded since WOMAC focuses on lower extremity function.

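### Accumulation is to be read from dose trends, which do not measure change over time, while the matched Day 1 and Day 15 profiles are never contrasted and run-in patients have no stated handling

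*Combined protocol and SAP*

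**What the plan says.** The PK Parameters entry of the synopsis states that Cmax and AUC trends against dose "will be analyzed within each patient group for any suggestion of drug accumulation or alterations in PK based on concomitant medications". Section 24.3 repeats this: the trends are examined "within each patient group for any suggestion of drug accumulation or alterations in PK based on concomitant medications". Neither place names a ratio between days, an occasion effect or a comparison of predose concentrations. Section 24.5 adds only a possible analysis of variance for a dose effect, where "The dependent variables for assessing dose proportionality will be estimates of selected PK parameters".

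The sampling schedule is richer than the analysis. For C1D15 and C1D16 in dose escalation, the synopsis says that "blood samples will be obtained once again for measurement of pexidartinib PK, using the same sampling times as on C1D1 and C1D2". Footnote 6 of the flow charts sets once-daily sampling at "predose (AM) and 0.5, 1, 2, 4, and 8 hours postdose on C1D(-7), C1D1 and C1D15". For twice-daily dosing, samples run to 7 hours after the morning dose, and then "The second dose will then be administered, and PK obtained 1 hour post the second dose (8 hours post the first dose"). Predose samples are also taken on C1D2, C1D8 and C1D16.

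In selected cohorts "3–6 patients will be treated with a pexidartinib dose of 100 mg QD during a one-week run-in period", and a further 3–6 patients receive 200 mg QD, before the full dose starts on C1D1. These patients have their own first-dose profile on C1D(-7). Footnote 6 plans no run-in with BID dosing.

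**The concern.** Accumulation asks whether exposure after repeated dosing exceeds exposure after the first dose in the same patient. The only method tied to that question is a trend against dose. If a patient group is a dose cohort, the assigned dose is constant and there is no trend to fit. If it spans doses, a common accumulation factor raises every point equally and leaves the slope alone.

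A second gap appears as soon as anyone forms the natural ratio. C1D1 is not a first-dose profile in run-in patients, and nothing in the plan says to separate them when PK is assessed by dose cohort. A ratio that uses their C1D1 as reference is too close to 1.

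PK is part of the primary objective of dose escalation (Section 8.1), and Section 6.3 suggests that human clearance may be slow. The description of accumulation in the final report should therefore rest on a contrast that measures it, with the run-in rule set in advance.

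**Working it through.** The plan gives no accumulation figure, so there is nothing of its own to reproduce. Three checks follow.

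**1. What a dose trend can show.** Write ln(exposure) = a + b·ln(dose) + ln(R), with R the same at every dose. R enters only the intercept. In a simulated data set (six assumed dose levels, six patients each), R = 1, 1.5, 2, 3 and 4 all gave b = 0.9455. The intercept rose from 0.359 to 1.745, a difference of 1.386 = ln 4.

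**2. Effect of the run-in on a C1D15/C1D1 ratio.** From the documents: run-in of 100 or 200 mg QD for 7 days; animal half-lives of 2–5 h (Section 6.3); no human half-life. Assumed: linear one-compartment oral model, ka = 1/h, full dose 300 mg QD, half-life 5, 10 or 20 h.

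Let a_i be the AUC that one unit dose contributes from 24i to 24i + 24 h, and r the run-in dose.
- C1D1 without run-in: 300·a_0
- C1D1 with run-in: 300·a_0 + r·(a_1 + … + a_7)
- C1D15: 300·(a_0 + … + a_14), plus r·(a_15 + … + a_21) for run-in patients

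| Half-life (assumed) | True ratio | C1D1 inflation, 100 mg / 200 mg | Ratio seen, 100 mg / 200 mg |
|---|---|---|---|
| 5 h | 1.04 | 1.4% / 2.9% | 1.03 / 1.01 |
| 10 h | 1.26 | 8.5% / 17% | 1.16 / 1.07 |
| 20 h | 1.82 | 27% / 55% | 1.43 / 1.18 |

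These are AUC over 0–24 h. Over 0–8 h, the once-daily interval in the fix, the 20 h case gives a true 1.90, seen as 1.46 after 100 mg or 1.19 after 200 mg. A simpler bolus model with a 24 h half-life shows the same pattern: a true 2.0 is seen as 1.5 or 1.2.

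**3. Precision of the ratio.** The 90% CI of a geometric mean ratio is the estimate multiplied and divided by exp[t(0.95, n−1)·√ln(1+CV²)·√(2/n)]. The within-patient CV is assumed.
- CV 30%, n = 6: exp(2.015 × 0.294 × 0.577) = 1.41; over CV 20–40%, 1.26 to 1.57
- CV 30%, n = 3: exp(2.920 × 0.294 × 0.816) = 2.01; over CV 20–40%, 1.6 to 2.5
- CV 30%, n = 30 pooled (an assumed number): 1.14

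Single cohorts are imprecise, which argues for pooling over dose levels.

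**The case against.** The sentence fixes no occasion and names accumulation as its aim, so comparing exposures between C1D1 and C1D15 may be what was meant. Accumulation that varies with dose would change the slope between days. Half-life is a planned parameter and, under linear PK, predicts an accumulation factor. These points stand. A reader might infer that the trial cannot detect accumulation at all; the documents do not support that, because the samples are collected and an indirect estimate is available. What remains is that the one method named is a dose trend and that no between-day contrast is written down.

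On the run-in, the plan contains no Day 15/Day 1 ratio for it to bias, and a true first-dose profile exists on C1D(-7). Only selected QD patients are affected. At the animal half-lives the distortion is at most about 3%. A reader might take the 1.82-seen-as-1.18 case as the expected bias, but it needs an assumed 20 h half-life and the larger run-in dose.

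On importance, a reader might infer that the dose or regimen choice is at risk. This version already sets the extension dose at 1000 mg/day on a BID regimen, and Section 24.5 calls the analyses generally descriptive, so a change of wording now does not bear on that choice.

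**Conclusion.** The point holds within limits. The named method does not measure change over time and, read on one occasion, carries no information on accumulation that is equal at every dose. That conclusion needs no half-life. The direct within-patient contrast can be formed from samples already scheduled in dose escalation, but not in the extension cohorts, where C1D1 has only a predose sample (Section 20.1).

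The run-in part is a warning about the choice of reference. Its direction, toward 1, is clear; its size runs from negligible to large across the assumed half-lives and cannot be fixed from the documents. Neither part touches the DLT rule or the extension decision rule.

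**What to change.** In the synopsis and Section 24.3, keep the dose-trend model for proportionality and keep the clause on PK alterations from concomitant medications. Add:

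> In dose-escalation patients, accumulation will be estimated as the within-patient C1D15/C1D1 ratio of Cmax and AUC over the common interval after the morning dose (0–8 h QD, 0–7 h BID), as geometric means with 90% CI, pooled over dose levels with regimen as a factor, and supported by the C1D2, C1D8 and C1D16 predose concentrations. Run-in patients are excluded from the primary ratio; a sensitivity analysis uses their dose-normalised C1D(-7) profile as reference, assuming dose proportionality.

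The BID interval stops at 7 h because the second dose precedes the 8 h sample. Dose-normalised C1D(-7) belongs in a sensitivity analysis because the synopsis treats dose proportionality as still to be explored; a departure from it would otherwise be read as accumulation.

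The cost is a few sentences and a short program. The downside is a little extra analysis and wide intervals for any single cohort of 3–6 patients.
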